8.1.3. Response Criteria

Efficacy evaluation will include the assessment of target and non-target tumor responses as well as objective responses. Responses will be assessed as defined in the Statistical Analysis Plan (SAP).

8.1.3.1. Target and Non-Target Response Assessments

Assessments will be based on the definitions for target and non-target lesions described in [Table 11](#).

Table 11: Target and Non-target Lesions

TARGET LESIONS	
Lesions Response:	Definition:
Complete Response (CR)	Disappearance of all target lesions. Any pathological lymph node must have reduction in short axis to <10 mm
Partial Response (PR)	At least a 30% decrease in the sum of diameters of the target lesions, taking as a reference the baseline sum diameters
Progressive Disease (PD)	At least a 20% increase in the sum of diameters of the target lesions, taking as a reference the smallest sum on study, including the baseline sum. In addition to the relative increase of 20%, the sum must also demonstrate an absolute increase of at least 5 mm. Definitive new lesion presence also indicates progression.
Stable Disease (SD)	Neither sufficient shrinkage to qualify for PR nor sufficient increase to qualify for PD, referencing the smallest sum diameters while on study.
NON-TARGET LESIONS	
Lesions Response:	Definition:
Complete Response (CR)	Disappearance of all non-target lesions and normalization of tumor marker level. All lymph nodes must be non-pathological in size (<10-mm short axis)
Partial Response (PR)	Persistence of one or more non-target lesion(s) and/or maintenance of tumor marker level above the normal limits
Progressive Disease (PD)	Unequivocal progression of existing non-target lesions (see following definition).

Abbreviations: CR=complete response; PD=progressive disease; PR=partial response; SD=stable disease

Progression in Non-target Disease: There must be an overall level of substantial worsening in non-target disease such that, even in the presence of SD or PR in target disease, the overall tumor burden has increased sufficiently to be considered as PD.

Because worsening in non-target disease cannot be easily quantified, a useful test that can be applied when assessing patients for unequivocal progression is to consider if the increase in overall disease burden based on the change in non-measurable disease is comparable in magnitude to the increase that would be required to declare PD for measurable disease (ie, an increase in tumor burden representing an additional 73% increase in “volume” [which is equivalent to a 20% increase in the diameter of a measurable lesion]).

When effusions are known to be a potential adverse effect of treatment, cytological confirmation of the neoplastic origin of any effusion that appears or worsens during treatment when the measurable tumor has met criteria for response or SD is not mandatory, but might be performed to differentiate between response (or SD) and PD when substantial change of effusion and/or ascites is noted.

If a patient is discontinued from the study before PD occurs and receives local or regional palliative radiotherapy during the follow-up period, the irradiation site must be omitted from the

response assessment of the patient; however, if the site is observed to demonstrate disease progression, this case should be judged as PD.

For equivocal findings of progression (eg, very small and uncertain new lesions; cystic changes or necrosis in existing lesions), treatment may continue until the next scheduled assessment. If at the next scheduled assessment, progression is confirmed, the date of progression should be the earlier date when progression was suspected.

8.1.4. Objective Response Assessment

Assessments will be based on the definitions provided in [Table 12](#) and [Table 13](#). Since this is a non-randomized study, all responses (CR/PR) must be confirmed.

Table 12: Time Point Response for Patients with Target (\pm Non-target) Disease

Target Lesions	Non-Target Lesions	New Lesions	Objective Response
CR	CR	No	CR
CR	Non-CR/Non-PD or Not all evaluated	No	PR
PR	Non-PD or Not all evaluated	No	PR
SD	Non-PD or Not all evaluated	No	SD
Not all evaluated	Non-PD	No	NE
PD	Any	Yes or No	PD
Any	PD	Yes or No	PD
Any	Any	Yes	PD

Table 13: Time Point Response for Patients with Only Non-target Disease

Non-Target Lesions	New Lesions	Objective Response
CR	No	CR
Non-CR/Non-PD	No	SD
Not all evaluated	No	NE
Unequivocal PD	Yes or No	PD
Any	Yes	PD

Abbreviations: CR=complete response; NE=not evaluable; PD=progressive disease; PR=partial response; SD=stable disease

The efficacy evaluation criteria described above will be used to derive the primary and secondary efficacy endpoints as defined in [Section 2](#).

8.2. Use of iRECIST to Guide Treatment Decisions

Until radiographic disease progression based on RECIST 1.1, there is no distinct iRECIST assessment. Upon documentation of PD per RECIST 1.1, patients who are clinically stable should not be discontinued until progression is confirmed by the Investigator, working with local radiology, according to the rules outlined in [Appendix D](#).

Clinical stability is defined as the following:

- Absence of symptoms and signs indicating clinically significant progression of disease
- No decline in ECOG performance status
- No requirements for intensified management, including increased analgesia, radiation, or other palliative care

Any patient deemed **clinically unstable** should be discontinued from study treatment at site-assessed first radiologic evidence of PD, and is not required to have repeat tumor imaging for confirmation of PD by iRECIST.

If the Investigator decides to continue treatment, the patient may continue to receive study treatment and the tumor assessment should be repeated 4 to 8 weeks later to confirm PD by iRECIST, per Investigator assessment. Images should continue to be sent in to the Sponsor.

If repeat imaging does not confirm PD per iRECIST, as assessed by the Investigator, and the patient continues to be clinically stable, study treatment may continue and follow the regular imaging schedule. If PD is confirmed, patients will be discontinued from study treatment.

If a patient has confirmed radiographic progression (iCPD) as defined in [Appendix D](#), study treatment should be discontinued; however, if the patient is achieving a clinically meaningful benefit, an exception to continue study treatment may be considered following consultation with the Sponsor. In this case, if study treatment is continued, tumor imaging should continue to be performed.

A description of the adaptations and iRECIST process is provided in [Appendix D](#), with additional details in the iRECIST publication ([Seymour et al. 2017](#)). A summary of imaging and treatment requirements after first radiologic evidence of progression is illustrated in [Figure 2](#).

[figure not shown]

Figure 2: Imaging and treatment for clinically stable patients treated with pembrolizumab after the first radiologic evidence of progression per RECIST 1.1

9. SAFETY EVALUATIONS

9.1. Adverse Events

An AE is defined as any untoward medical occurrence in a clinical study patient and does not necessarily have a causal relationship with the study drug. An AE can therefore be any unfavorable and unintended sign (including an abnormal finding), symptom, or disease temporally associated with the use of a study drug, whether or not related to the study drug. This includes any occurrence that is new in onset or aggravated in severity or frequency from the baseline condition, or abnormal results of diagnostic procedures, including laboratory test abnormalities.

All AEs will be collected from the time the ICF is signed through 30 days after the last dose of any study therapy (safety follow-up) or until the start of new antitumor therapy, whichever is earlier; SAEs will be collected through 90 days after the last dose of any study therapy. For all AEs that occur between signing ICF and first dose of study therapy, there is no need to record those that are unrelated unless it is mandatory by local regulations. All AEs will be documented in the eCRF. Any untoward medical event that occurs after the safety follow-up is not considered an AE, unless the Investigator considers that the AE is related to the study drug. Serious AEs related to study therapy will be collected through the survival follow-up.

Signs and symptoms of a pre existing disease should not be considered an AE, but should rather be considered baseline signs and symptoms. Clinically significant worsening of pre existing signs and symptoms is considered an AE.

For definitions and reporting of pregnancies, overdoses, and medication errors, refer to [Section 9.5](#).

9.2. Reporting of Adverse Events

9.2.1. Terms of Reported Adverse Events

All AEs will be documented in the eCRF according to the eCRF Completion Guidelines. Documentation should include onset and resolution/stabilization dates, severity/grade, relationship to study drug, and outcome of the event. However, all SAEs must be reported on an SAE form as per the SAE form completion guidelines, as well as in the eCRF.

When a diagnosis for the reported signs or symptoms is known, the Investigator should report the diagnosis, not the symptoms, as the AE.

Adverse events can be spontaneously reported or elicited during open-ended questioning, examination, or evaluation of a patient. In order to prevent reporting bias, patients should not be questioned regarding the specific occurrence of one or more AEs.

9.2.2. Severity of Adverse Events

The NCI-CTCAE Version 5.0 will be used to grade the severity of AEs.

9.2.3. Causal Relationship with Study Drug

The causal relationship between an AE and study drug will be assessed using the following 2-point scale, taking into account the patient's condition, medical history, concomitant medications, and the temporal relationship between study drug administration and onset of the event.

1. An AE is considered to be "**Related**" if the event follows a reasonable temporal sequence from administration of study drug and there is a **reasonable possibility** that at least one of the following conditions is true:
 - A positive dechallenge: This means that the event improves or resolves after the drug is stopped (temporarily or permanently).
 - A positive rechallenge: This means that the event reappears after the drug is restarted.
 - The event cannot be reasonably explained by the patient's clinical state and/or other therapies administered.
 - A single occurrence of an event that is uncommon and known to be strongly associated with drug exposure (eg, angioedema, Stevens-Johnson syndrome).
2. An AE is considered to be "**Not related**" if there is **no reasonable possibility** that at least one of the following conditions is true:
 - The event occurred prior to study drug administration.
 - There is no reasonable possibility that the study drug caused the event. ("no reasonable possibility" means there is no evidence to suggest a causal relationship between the study drug and the AE)
 - The event does not follow a reasonable temporal sequence from administration of study drug and could have been produced by a documented pre-existing condition, concomitant medication or patient's clinical state.

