5.2. Definition of Dose-Limiting Toxicity

For this study, unacceptable toxicity will include any event meeting the criteria for dose-limiting toxicity (DLT), as outlined below. An adverse event not meeting the criteria for a DLT may also be considered an unacceptable toxicity, if it is not tolerable in the long-term and necessitates discontinuation of one or more elements of the combination therapy.

DLT Definition

All toxicities will be graded using the National Cancer Institute – Common Terminology Criteria for Adverse Events (NCI-CTCAE) Version 5.0, based on Investigator assessment. The occurrence of any of the following toxicities during Cycle 1 will be considered a DLT, if assessed by the Investigator to be related to study treatment administration.

- Grade 4 nonhematologic toxicity (not laboratory)
- Grade 4 neutropenia lasting >5 days
- Grade 4 thrombocytopenia of any duration

- Grade 3 thrombocytopenia associated with clinically significant bleeding
- Any nonhematologic AE \geq Grade 3 in severity, with the following exceptions:
 - Grade 3 fatigue lasting \leq 3 days;
 - Grade 3 diarrhea, nausea, or vomiting without use of anti-emetics or anti-diarrheals per standard of care;
 - Grade 3 rash without use of corticosteroids or anti-inflammatory agents per standard of care.
- Any Grade 3 or Grade 4 nonhematologic laboratory value if:
 - Clinically significant medical intervention is required to treat the patient, or
 - The abnormality leads to hospitalization, or
 - The abnormality does not recover to Grade \leq 1 within 48 hours despite best supportive care, or
 - The abnormality results in a drug induced liver injury
 - Exceptions: clinically nonsignificant, treatable, or reversible laboratory abnormalities including liver function tests, uric acid, hyperphosphatemia, etc.
- Febrile neutropenia Grade 3 or Grade 4:
 - Grade 3 is defined as ANC $<1000/\text{mm}^3$ with a single temperature of $>38.3^\circ\text{C}$ (101°F) or a sustained temperature of $\geq38^\circ\text{C}$ (100.4°F) for more than 1 hour
 - Grade 4 is defined as ANC $<1000/\text{mm}^3$ with a single temperature of $>38.3^\circ\text{C}$ (101°F) or a sustained temperature of $\geq38^\circ\text{C}$ (100.4°F) for more than 1 hour, with life-threatening consequences and urgent intervention indicated.
- Grade 3 or higher visual impairment
- Prolonged delay (>2 weeks) in initiating Cycle 2 due to treatment-related toxicity

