11.5.4. Safety Analyses

The safety analyses will be performed by each cohort and study drug using the All Treated Population.

All AEs will be summarized (by incidence) and listed by the System Organ Class, Preferred Term, toxicity/severity grade, and causal relationship to futibatinib. In addition, separate summaries of SAEs and Grade 3 or 4 AEs will be presented.

For all AEs that occurred between the signing of the ICF and the last day of the Safety Follow-up Period, lists of preferred AE terms, grade, onset date, actions, outcome of AE, date of outcome confirmed, causalities with the study drug, and comments on AEs will be listed by patient.

Hematological and chemistry laboratory parameters will be graded according to the NCI-CTCAE (Version 5.0) where applicable. The worst severity grade, time to maximum Grade 3 or 4 value, and time to resolution (return to baseline grade or below) will be summarized.

A list of 12-lead ECG findings will be presented by patient.

11.5.5. ^{CCI} [REDACTED] Analysis

^{CCI} [REDACTED] data will be listed by cohort using the All Treated Population.

11.5.6. ^{CCI} [REDACTED] Analysis

The ^{CCI} [REDACTED] analyses will be performed using the ^{CCI} [REDACTED] data will be summarized descriptively as described in a separate SAP.

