5.5.2.2. Adverse Events

AE is any untoward medical condition that occurs in patients while participating in this clinical study. Adverse events will be coded according to the MedDRA (the most up-to-date version at the time of analysis) terminology and the severity of the toxicities will be graded according to NCI CTCAE (Version 5.0), where applicable.

An on-treatment AE is defined as an AE that is starting or worsening at the time of or after the first dose of study drug administration and within 30 days after the last dose of study drug, and do not necessarily have a causal relationship to the use of the study drug. All AEs captured in the database will be listed; however, only on-treatment AEs will be summarized.

The following AE summary tables will be generated:

- 1) Summary of AEs with the number and percentage of patients reporting AEs, serious AEs, grade ≥ 3 AEs, AEs leading to study drug discontinuation, interruption and dose reduction, and AEs with outcome of deaths.
- 2) Summary of treatment-related AEs with the number and percentage of patients reporting AEs, serious AEs, grade ≥ 3 AEs, AEs leading to study drug discontinuation, interruption and dose reduction, and AEs with outcome of deaths.
- 3) Summary of AEs by worst CTCAE Grade (grade 1, 2, 3, 4, 5, any grade, Grade ≥ 3) presented by System Organ Class (SOC) and Preferred Term (PT).
- 4) Summary of treatment-related AEs by worst CTCAE grade (Grade 1, 2, 3, 4, 5, any grade, Grade ≥ 3) presented by SOC and PT.
- 5) Summary of AEs leading to death by SOC and PT.
- 6) Summary of the most common AEs ($\geq 10\%$ incidence) and median time to first AE by SOC and PT.

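### Protocol 9.2.3 defines *Not related* the wrong way round, and the protocol's AE causality summary names only one of the two study drugs

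*Protocol*

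**What the plan says.** **The causality scale.** Protocol 9.2.3 has two categories. An AE is *Related*, the text says, "if the event follows a reasonable temporal sequence from administration of study drug and there is a reasonable possibility that at least one of the" listed signs of drug causation is present (dechallenge, rechallenge, no other reasonable explanation, or a rare event strongly tied to drug exposure). It is *Not related* "if there is no reasonable possibility that at least one of the following conditions is true". Three conditions follow: "The event occurred prior to study drug administration"; "There is no reasonable possibility that the study drug caused the event"; and, third, no reasonable temporal sequence together with another documented possible cause.

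**The analyses.** Protocol 11.5.4 and the synopsis (Safety Analyses) summarize and list all AEs by System Organ Class, Preferred Term, "toxicity/severity grade, and causal relationship to futibatinib". The by-patient listing in the same sections refers instead to causality with the study drug. Protocol 5.2 counts a Cycle 1 toxicity as dose-limiting "if assessed by the Investigator to be related to study treatment administration". SAP 5.5.2.2 plans a "Summary of treatment-related AEs with the number and percentage of patients reporting AEs", and SAP 5.5.2.2 to 5.5.2.5 add related-event tables by grade, for discontinuations, for dose modifications and for SAEs. SAP 6.4 and 6.5 speak of drug-related events. The SAP defines neither term for a two-drug regimen, and SAP 8 declares no changes to the planned analyses.

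**The concern.** Two separate defects bear on the same data item.

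First, the *Not related* definition places a negative lead-in over conditions that already point to non-relatedness. An investigator who follows the sentence reaches the opposite of what the conditions say.

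Second, the protocol's causality summary leaves out one of two study drugs. The stated safety objective is the combination, and Protocol 5.3.3.1 with Table 8 is given over to immune-related events of pembrolizumab. An event attributed only to pembrolizumab would not appear as related in that summary.

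Relatedness also governs what is collected. Protocol 9.1 does not require unrelated pre-dose AEs to be recorded and collects related SAEs through survival follow-up. Protocol 3.2 limits assessment after the 30-day visit to therapy-related SAEs in patients not yet on new anticancer therapy. Protocol 3.2.5 limits the non-serious AEs that must be collected in the extension to those that are related or lead to discontinuation. Protocol 5.3.3.1 warns that immune events may appear months after the last pembrolizumab dose. An event that is not collected because its causality was unclear cannot be restored at analysis.

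**Working it through.** The plan gives no figure on this point, so the check is one of logic and of matching terms.

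**Step 1: the two categories applied to clear cases.** Item 1 is met if there is a reasonable temporal sequence and at least one sign of causation is reasonably possible. Item 2, as written, is met if none of its three conditions is reasonably possible. As reworded in the fix, it is met if at least one of the three is true.

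| Event | Item 1 met (*Related*) | Item 2 condition plausible | *Not related*, as written | *Not related*, as reworded |
|---|---|---|---|---|
| Onset before dosing | No | Yes | No | Yes |
| After dosing, no plausible sequence, explained by a pre-existing illness | No | Yes | No | Yes |
| After dosing, positive dechallenge and rechallenge, no other explanation | Yes | No | Yes | No |

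The *as written* column is inverted in every row. The first two events have no category (a gap). The third has both (an overlap). The second listed condition is already a negative, so under this lead-in it becomes a double negative.

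Under the rewording each clear case falls in exactly one category. The first and third conditions contradict item 1's temporal requirement, and the second contradicts its requirement of a reasonable possibility.

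**Step 2: the causality terms side by side.**

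| Place | Causality is to |
|---|---|
| Protocol 5.2 (dose-limiting toxicity) | study treatment |
| Protocol 9.2.1 and 9.2.3 (recording and grading of causality) | study drug |
| Protocol 11.5.4 and synopsis, AE summary | futibatinib only |
| Protocol 11.5.4 and synopsis, by-patient listing | study drug |
| SAP 5.5.2.2 to 5.5.2.5 | treatment, undefined |
| SAP 6.4 and 6.5 | drug, undefined |

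Only the protocol's AE summary is limited to one agent. Protocol 11.5.2 presents exposure separately for futibatinib and pembrolizumab, so the plan does not generally treat study drug as meaning futibatinib.

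**Step 3: which outputs each defect reaches.**

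- *Dose-limiting toxicity.* The test is relation to study treatment, so the futibatinib wording plays no part. Protocol 5.2 also lets a non-DLT event count as unacceptable toxicity if it is intolerable in the long term and forces discontinuation of part of the combination, with no causality condition stated.
- *SAP related-AE tables.* They are not restricted to futibatinib. They contain on-treatment events only (SAP 5.5.2.2 and 6.2), so pre-dose events do not enter them.
- *Protocol 11.5.4 and synopsis summary.* Followed as written, it omits from the related counts any event attributed only to pembrolizumab.
- *Causality data.* The literal overlap permits a clearly related on-treatment event to be recorded either way. The documents give no rate of such misclassification and no split of attribution between the drugs.

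**The case against.** The best defence is that nobody would be misled. The conditions in item 2 make the intent obvious, its second condition explains what no reasonable possibility means, and Protocol 9.1 takes for granted that a pre-dose event can be unrelated. Item 1 is sound, and it is *Related* that drives both dose-limiting toxicity and the related-AE tables. The futibatinib phrase names one dimension of one summary and does not define relatedness. Protocol 11 sends detailed methods to the SAP, whose tables use the broader term, and all-causality tables by grade, System Organ Class and Preferred Term are planned as well.

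Most of this stands, and it rules out three stronger readings that a reader might infer:

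- *That DLT attribution covers futibatinib only.* Protocol 5.2 says otherwise.
- *That the SAP's related-AE rates are wrong or understate the regimen's toxicity.* The tables are not limited to one drug. The term is undefined, which is a lesser fault.
- *That the inversion would tip the safety rule.* A rule applied to six or ten patients is sensitive to any single event, but neither defect produces a determinate reclassification, and a pre-dose event cannot be a Cycle 1 DLT.

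What the defence does not remove is the text itself. This is the protocol's only definition of *Not related*, and it says the reverse of what is meant. The protocol's causality summary still leaves out a study drug, and SAP 8 declares no change that would acknowledge the broader term.

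**Conclusion.** Both passages are wrong as written, with limited scope. Item 2 of Protocol 9.2.3 is logically inverted, so the two causality categories overlap and leave a gap. The AE causality summary in Protocol 11.5.4 and the synopsis would, if followed, omit events attributed only to pembrolizumab, while the SAP's treatment-related has no definition for two drugs. The consequence is possible misclassification and an incomplete protocol summary, not a demonstrated error in any count or rate. No magnitude can be computed, because the documents give neither attribution frequencies nor a misclassification rate. The conclusion rests on the literal text and on study drug covering both agents, as Protocol 5.7 and 11.5.2 indicate.

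**What to change.** - **Protocol 9.2.3, item 2.** Replace the lead-in with: *An AE is considered Not related if at least one of the following conditions is true.* The three conditions can stay.
- **Protocol 11.5.4 and synopsis.** Change the causality dimension of the AE summary from futibatinib to study treatment.
- **SAP 5.5.2.2.** Define treatment-related as related to futibatinib, pembrolizumab or both, and use the same term in SAP 6.4 and 6.5 in place of drug-related.
- **Tables.** Where the eCRF records causality for each drug, tabulate related events by drug as well as for either drug. The documents do not show whether it does.

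The cost is a wording change in the protocol and SAP and, at most, a few extra columns in planned tables. No dose, clinical rule, endpoint or sample size is affected.
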